### **8.8 Source Data**

Source documents are original documents, data, and records from which participants' CRF data are obtained. These include, but are not limited to, hospital records (from which medical history and previous and concurrent medication may be summarised into the CRF), clinical and office charts, laboratory and pharmacy records, diaries, microfiches, radiographs, and correspondence.

CRF entries will be considered source data if the CRF is the site of the original recording (e.g. there is no other written or electronic record of data).

All documents will be stored safely in confidential conditions. On all study-specific documents, other than the signed consent, the participant will be referred to by the study participant number/code, not by name.

## **9. TREATMENT OF TRIAL PARTICIPANTS**

### **9.1 Storage of Study Equipment of Related Apparatus**

All study specific equipment is stored in a research-dedicated lab, and the Department of Medical Physics, University of Leicester is responsible for the service and maintenance of the equipment.

### **9.2 Clinical Care**

Throughout the study, patients with MCI, VascD and AlzD will continue to receive standard clinical care.

### **9.3 Incidental Findings**

Any unexpected or incidental findings in Volunteers or Patients, such as, high blood pressure, abnormal heart rhythm, undiagnosed cognitive impairment (volunteers), cerebral blood flow velocity suggestive of intracranial pathology or carotid artery stenosis will be reported to the patient or volunteer's GP for further investigation. This will only be with the patient or volunteer's permission and written consent (*Participant (Patient or Volunteer) Consent Form*), and is expressly stated in the *Participant (Patient or Volunteer) Information Sheet*.

## **10. SAFETY REPORTING**

### **10.1 Definitions**

#### **Adverse Event (AE)**

An AE or adverse experience is:

Any untoward medical occurrence in a patient or clinical investigation participant, which does not necessarily have to have a causal relationship with his/her treatment.

An AE can therefore be any unfavourable and unintended sign (including an abnormal laboratory finding), symptom or disease temporally associated with the study, whether or not considered related to the study.

#### **Adverse Reaction (AR)**

All untoward and unintended responses related to the study.

All cases judged by either the reporting medically qualified professional or the sponsor as having a reasonable suspected causal relationship to the study qualify as adverse reactions.

#### **Severe Adverse Events (SAE)**

To ensure no confusion or misunderstanding of the difference between the terms “serious” and “severe”, which are not synonymous, the following note of clarification is provided:

The term “severe” is often used to describe the intensity (severity) of a specific event (as in mild, moderate, or severe myocardial infarction); the event itself, however, may be of relatively minor medical significance (such as severe headache). This is not the same as “serious”, which is based on patient/event outcome or action criteria usually associated with events that pose a threat to a participant’s life or functioning. Seriousness (not severity) serves as a guide for defining regulatory reporting obligations.

#### **Serious Adverse Event or Serious Adverse Reaction (SAR)**

A serious adverse event or reaction is any untoward medical occurrence that:

- Results in death
- Is life-threatening

NOTE: The term "life-threatening" in the definition of "serious" refers to an event in which the participant was at risk of death at the time of the event; it does not refer to an event which hypothetically might have caused death if it were more severe.

- Requires inpatient hospitalisation or prolongation of existing hospitalisation
- Results in persistent or significant disability/incapacity, or
- Is a congenital anomaly/birth defect
- Other important medical events\*

\*Other events that may not result in death, are not life threatening, or do not require hospitalisation, may be considered a serious adverse event when, based upon appropriate medical judgement, the event may jeopardise the patient and may require medical or surgical intervention to prevent one of the outcomes listed above.

#### **Expected Serious Adverse Events/Reactions**

Serious adverse events are common in dementia. For a full list of expected SAE that are not subject to expedited reporting, investigators should refer to Appendix A.

#### **Suspected Unsuspected Serious Adverse Events/Reactions (SUSAR)**

A serious adverse event, the nature or severity of which is not consistent with a diagnosis of dementia.

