### 3. ABBREVIATIONS

ACE-III	Addenbrooke's Cognitive Examination
AE	Adverse event
AlzD	Alzheimer's Dementia
AR	Adverse reaction
ARI	Autoregulation Index
BP	Arterial Blood Pressure
CA	Cerebral Autoregulation
CBF	Cerebral Blood Flow
CBFv	Cerebral Blood Flow Velocity
CI	Chief Investigator
CPP	Cerebral Perfusion Pressure
CrCP	Critical Closing Pressure
CRF	Case Report Form
CRO	Contract Research Organisation
CT	Clinical Trials
CVR	Cerebrovascular Resistance
CVRi	Cerebrovascular Resistance Index
dCA	Dynamic Cerebral Autoregulation
EC	Ethics Committee (see REC)
ECG	Electrocardiogram
EHI	Edinburgh Handedness Inventory
EtCO 2	End-Tidal Partial Pressure of Carbon Dioxide
FFT	Fast Fourier Transform
GCP	Good Clinical Practice
GP	General Practitioner
GPI	Gosling's Pulsatility Index
HC	Healthy Control
HR	Heart Rate
ICH	International Conference on Harmonisation of Technical Requirements for Registration of Pharmaceuticals for Human Use
ISF	Investigator Site File
LRI	Leicester Royal Infirmary
MCA	Middle Cerebral Artery
MCI	Mild Cognitive Impairment
NVC	Neurovascular Coupling
NHS	National Health Service
NICE	National Institute for Health and Care Excellence

NRES	National Research Ethics Service
PET	Positron Emission Tomography
PI	Principal Investigator
PIL/S	Participant/ Patient Information Leaflet/Sheet
RAP	Resistance Area Product
R&D	NHS Trust R&D Department
REC	Research Ethics Committee
SAE	Serious Adverse Event
SAR	Serious Adverse Reaction
SOP	Standard Operating Procedure
SUSAR	Suspected Unexpected Serious Adverse Reactions
TCD	Transcranial Doppler Ultrasound
TFA	Transfer Function Analysis
TMF	Trial Master File
UK	United Kingdom
VMR	Vasomotor Reactivity
VascD	Vascular Dementia

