### **10.3 Reporting Procedures for Serious Adverse Events**

All SAEs, must be reported to the Sponsor within one working day of discovery or notification of the event. The Sponsor will perform an initial check of the information and ensure that it is reviewed at the next R&D Management meeting. All SAE information must be recorded on an SAE form and sent to the Sponsor using the appropriate reporting form and the contact details on there. Additional information received for a case (follow-up or corrections to the original case) needs to be detailed on a new SAE form which must be sent to the Sponsor using the appropriate reporting form and the contact details on there.

The Sponsor will report all SUSARs to the Research Ethics Committee concerned. Fatal or life-threatening SUSARs must be reported within 7 days and all other SUSARs within 15 days. The CI will inform all investigators concerned of relevant information about SUSARs that could adversely affect the safety of participants.

In addition to the expedited reporting above, the CI shall submit once a year throughout the study or on request an Annual Report to the Ethics Committee which lists all SAEs / SUSARs that have occurred during the preceding 12 months.

Only SAEs that occur during the fTCD study will be reported to the sponsor. After this, the Patient or Volunteer, ceases to be involved in the study.

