**20. APPENDIX A: EXPECTED EVENTS NOT SUBJECT TO EXPEDITED REPORTING**

Acute Coronary Syndromes	Myocardial infarction
Agitation	Nausea
Angina	Personality change
Anorexia	Peripheral Vascular Disease
Anxiety	Renal impairment
Constipation	Sedation
Delirium	Seizure
Depression	Sexual dysfunction
Dysphagia	Sleep disturbance
Electrolyte disturbance	Stroke
Fall	Transient ischemic attack
Fatigue	Urinary retention
Gastrointestinal disturbance	Urinary tract infection
Hallucinations	Violent behaviour
Incontinence, faecal	Visual loss
Incontinence, urinary	Vomiting
Infections	Weakness
Institutionalisation / Admission to care home	Weight loss
Intracerebral Haemorrhage	
Loss of ability to function or care for self	

[figure not shown]
[figure not shown]

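### Reporting to the ethics committee does not use relatedness, so a study-related serious event listed in Appendix A need not be expedited to the committee

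*Combined protocol and SAP*

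**What the plan says.** Section 3 expands SUSAR as "Suspected Unexpected Serious Adverse Reactions". Section 10.1 defines an adverse reaction as "All untoward and unintended responses related to the study", on the judgement of a medically qualified professional or the sponsor. Under the SUSAR heading, however, 10.1 gives a different test: "A serious adverse event, the nature or severity of which is not consistent with a diagnosis of dementia".

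Section 10.1 notes that serious events are common in dementia and then exempts a list: "For a full list of expected SAE that are not subject to expedited reporting, investigators should refer to Appendix A". The appendix is headed "EXPECTED EVENTS NOT SUBJECT TO EXPEDITED REPORTING" and includes fall, seizure, stroke, intracerebral haemorrhage and myocardial infarction. No entry carries a condition on relatedness.

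Section 10.2 has a medically qualified investigator assess relatedness for each adverse event. Related events are followed until they resolve or stabilise.

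Section 10.3 sends every SAE to the sponsor within one working day, with review at the next R&D Management meeting. For the ethics committee, "The Sponsor will report all SUSARs to the Research Ethics Committee concerned", and "Fatal or life-threatening SUSARs must be reported within 7 days and all other SUSARs within 15 days". Separately, the chief investigator is to "submit once a year throughout the study or on request an Annual Report to the Ethics Committee", listing the SAEs and SUSARs of the preceding 12 months. The synopsis plans a trial period of 7 months. Section 16 states that no data safety monitoring committee is needed.

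**The concern.** An ethics committee most needs to hear of serious events that the study procedure may have caused. The protocol collects the judgement that would identify them, but the rules on what the committee receives do not use it. The expedited trigger asks whether an event fits the disease. Many events that fit the disease could also arise from a laboratory session with frail or cognitively impaired people. A fall on leaving the couch that leads to admission is an example.

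Such an event would be exempt from expedited reporting because it is listed. An unrelated serious event that is off the list and does not fit dementia would start a 7- or 15-day clock. If the only other scheduled report is yearly and the trial lasts 7 months, the committee might not learn of the related event while recruitment continues.

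**Working it through.** No power or error-rate figure is involved. The check traces the reporting rules and compares two time intervals.

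**Step 1: does relatedness change the expedited route?** Take a serious event in a participant with dementia and apply 10.1, 10.3 and Appendix A as written.

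| Event | Judged related? | Expedited to the committee? |
|---|---|---|
| Listed in Appendix A | Yes | No |
| Listed in Appendix A | No | No |
| Not listed, not consistent with dementia | Yes | Yes, 7 or 15 days |
| Not listed, not consistent with dementia | No | Yes, 7 or 15 days |

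Within each pair of rows the relatedness answer differs and the outcome is the same. In the fall example, admission makes the event serious under 10.1, a judgement of relatedness makes it a reaction under 10.1, and its place on the list exempts it.

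**Step 2: how wide is the exemption?** Counting the two columns of Appendix A gives 20 + 18 = 38 entries.

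**Step 3: do the exemption and the definition agree?** Not always, for two reasons.

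- The definition refers to nature or severity. A listed event of unusual severity could therefore be a SUSAR, while the exemption of listed events has no such qualification.
- The benchmark is dementia. Healthy controls must show no memory impairment, and MCI patients must not be demented (section 7.3). That is 11 + 11 = 22 of the 4 × 11 = 44 planned participants. A stroke in a healthy control is arguably a SUSAR under the definition and yet exempt under the list.

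**Step 4: does the Annual Report fall due?** Let L be the number of months by which the reporting clock starts before the trial. The documents do not give L, so it is an assumption. The first report is due in trial month 12 − L, and it falls within the planned period if 12 − L ≤ 7, that is, if L ≥ 5.

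| L (months) | First report due in trial month | Within 7 months? |
|---|---|---|
| 0 | 12 | No (5 months after the planned end) |
| 4 | 8 | No |
| 5 | 7 | Yes |
| 8 | 4 | Yes, but it covers only events up to month 4 |

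**Result.** A related serious event that is exempt as listed has no expedited route to the committee. It has no scheduled route within the planned period if L is below 5, and one possible scheduled report if L is 5 to 12. The unscheduled route, a report on request, is always available. Section 8.6 describes an end-of-study letter to participants, and no end-of-trial safety report to the committee is described.

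**The case against.** The strongest case on the other side is that oversight exists and the exposure is small. Every SAE, listed or not and related or not, goes to the sponsor within one working day and is reviewed at an R&D meeting. Section 13 adds risk-based monitoring. A reader might infer from the SUSAR wording that a study-caused harm would get no review beyond the research team. The documents do not support that; the gap concerns the ethics committee only.

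A reader might also infer that the causality judgement has no effect. It does: 10.2 uses it to decide how long an event is followed. What holds is that it plays no part in reporting to the committee.

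It can also be argued that the word reaction in the SUSAR name implies causality, so the fault is loose drafting. That is possible, but the operative sentence contains no such test, and the heading above it speaks of events as well as reactions. Sections 13, 14.2 and 14.4 bind the study to GCP, regulations and sponsor procedures that may impose further duties. Their content is not given, so the point is limited to what this protocol's text requires.

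Expediting unrelated events is over-reporting and hides nothing. Few events are likely: if reportable SAEs are those during sessions of about 90 minutes, 44 first visits plus 11 repeats give 55 × 1.5 = 82.5 hours of non-invasive observation. This bears on how urgent the change is, but it does not remove the misrouting.

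**Conclusion.** The point holds for the ethics committee route. Relatedness is defined and assessed but does not enter the SUSAR definition, the exemption of 38 listed events, or the rules for what the committee receives. On this text a study-related serious event on Appendix A need not be expedited to the committee.

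Two stronger readings go too far. It is not certain that no yearly report falls within the trial. That is so if the clock starts with the trial, or less than 5 months before it, and if the trial keeps to 7 months. Nor is every listed event cleanly exempt in every participant. For the 22 without dementia, and for events of unusual severity, the exemption and the definition conflict and must be reconciled.

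This should be corrected, but it is a matter of wording in a low-risk observational study. No estimate, test or sample size is affected.

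**What to change.** - In 10.1, define the expedited category as a serious event that the medically qualified investigator or the sponsor judges related to the study, using the protocol's own adverse-reaction definition, and that is unexpected. Say what unexpectedness is judged against in all four groups: Appendix A is drawn up from dementia, and the protocol has no list of events expected from the study procedures.
- In 10.1 and Appendix A, state that the exemption applies only to events judged unrelated to the study, so that a related event is not exempt merely because it is listed. Reconcile this with the SUSAR definition and with 10.3.
- In 10.3, keep the annual and on-request reports, state when the yearly clock starts, and add one end-of-trial listing to the ethics committee of all SAEs with their relatedness. Replacing the annual provision instead could drop the on-request route.

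The cost is revised wording in 10.1, 10.3 and Appendix A and one listing, with few events expected from 44 participants. Unrelated events would no longer need 7- or 15-day reports. Design, assessments and analysis are unchanged.

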**2. SYNOPSIS**

Study Title	Cerebral Haemodynamic Changes During Cognitive Testing: A Functional Transcranial Doppler (fTCD) study
Internal ref. no.	
Trial Design	Prospective, observational, case-control study
Trial Participants	Healthy Control Subjects, Patients with Mild Cognitive Impairment, Patients with Vascular Dementia and Patients with Alzheimer’s Dementia
Planned Sample Size	11 Healthy Control Patients, 11 Patients with Mild Cognitive Impairment, 11 Patients with Vascular Dementia and 11 Patients with Alzheimer’s Dementia
Follow-up duration	None
Planned Trial Period	7 Months
Primary Objective	To compare the beat-to beat cerebral blood flow velocity (CBFv) between patients with Mild Cognitive Impairment (MCI), patients with Vascular Dementia (VascD), patients with Alzheimer’s Dementia (AlzD) and age-, gender- and blood pressure (BP)-matched healthy control (HC) subjects during performance of the Addenbrooke’s Cognitive III (ACE-III) examination
Secondary Objectives	
 
1) To investigate whether performance of the Addenbrooke’s Cognitive III Examination is associated with differences in other beat-to-beat cerebral haemodynamic parameters, specifically autoregulation index (ARI), between MCI patients, VascD patients, AlzD patients, and age-, gender- and BP-matched HC subjects.
 
2) To assess the acceptability and feasibility of this protocol in patients with cognitive impairment in clinical practice.
 
3) To assess the reproducibility of measurements in cognitively impaired patient group at 3 months from initial measurement
 

Outcome Measure	
This is not an intervention study, and therefore it would not be appropriate to assess the classical primary and secondary outcome measures such as death and disability for this study. However, we intend to evaluate the following relevant outcomes:
 
 
1. The percentage of recruited subjects (HC, MCI patients, VascD patients and AlzD patients) able to comply with the full measurement protocol.
 
2. The percentage of measurements rejected because of aspects related to data quality during the analysis protocol, with recorded reasons.
 
3. Overall, the percentage of recruited subjects (healthy controls, MCI patients, VascD patients and AlzD patients) in whom values for the following parameters can be derived:
 

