#### **Healthy Controls-specific Inclusion Criteria**

- No evidence of subjective or objective memory impairment on cognitive testing
- No major medical co-morbidity (outlined in detail in the exclusion criteria) or medication use that could adversely affect cognition

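### Section 10.1 and Appendix A judge expectedness only against dementia, do not say which groups they cover, and can conflict for the 22 of 44 planned participants who have no dementia

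*Combined protocol and SAP*

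**What the plan says.** Four parts of the combined protocol and SAP bear on this.

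- **Section 10.1, SUSAR.** One definition serves all participants: "A serious adverse event, the nature or severity of which is not consistent with a diagnosis of dementia".
- **Section 10.1, Expected Serious Adverse Events/Reactions.** The reason given for an expected list is that "Serious adverse events are common in dementia". The section continues: "For a full list of expected SAE that are not subject to expedited reporting, investigators should refer to Appendix A".
- **Section 20.** The list is headed "APPENDIX A: EXPECTED EVENTS NOT SUBJECT TO EXPEDITED REPORTING". It is not divided by group. It contains "Intracerebral Haemorrhage", and also stroke, myocardial infarction and seizure.
- **Section 10.3.** Every SAE goes to the sponsor within one working day. The faster route to the ethics committee is for SUSARs only: "Fatal or life-threatening SUSARs must be reported within 7 days and all other SUSARs within 15 days". All SAEs are also listed in a report to the committee each year or when it asks.

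The planned sample in the Synopsis includes "11 Healthy Control Patients, 11 Patients with Mild Cognitive Impairment". Section 7.3 requires controls to show "No evidence of subjective or objective memory impairment on cognitive testing" and requires MCI patients to be free of dementia.

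**The concern.** Expectedness decides whether a serious event reaches the ethics committee quickly. The only yardstick given is a diagnosis that half the planned participants do not have, and no section gives controls or MCI patients a different one. Two investigators could therefore read the same protocol and classify the same stroke in a volunteer differently. At stake is the 7- or 15-day report to the committee for a listed serious event in someone without dementia. It is the only time-limited external safety report in the plan, and Section 16 provides for no data safety monitoring committee.

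**Working it through.** There is no stated figure to reproduce. The check sets the rules side by side and then sizes their reach.

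**1. Who is covered.** From the Synopsis there are 4 groups of 11, so 4 × 11 = 44. Without dementia by eligibility: 11 controls + 11 MCI = 22, and 22 / 44 = 50%.

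**2. A stroke or intracerebral haemorrhage in one of these 22.**

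| Rule | Test applied | Result |
|---|---|---|
| SUSAR definition (10.1) with 10.3 | Is the event consistent with a diagnosis of dementia? The person has no such diagnosis, so no. | SUSAR: 7 days if fatal or life-threatening, otherwise 15 |
| Expected SAEs (10.1) with Appendix A | Is the event on the list? Yes. | No expedited report |

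The results are opposite, and no section ranks one rule above the other.

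The definition can also be read as asking whether the event is of a kind seen in dementia. The two rules then agree, but only by measuring a person without dementia against dementia. Either way the text needs to say what applies to these groups.

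**3. What is lost if Appendix A is followed.** Only the 7/15-day report to the ethics committee. Notice to the sponsor within one working day does not depend on expectedness. The yearly listing remains too, but the Synopsis plans a 7-month trial. If the reporting year starts with the trial, the first yearly report falls 12 − 7 = 5 months after the planned end, unless the committee asks sooner.

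**4. How much exposure is involved.** Section 10.3 limits SAE reporting to events during the fTCD study. If that means the assessment sessions, Section 6.1 gives one session of about 90 minutes (1.5 hours), and Section 8.5 adds a repeat for a subset of 11. Assume that a repeat lasts as long as the first session, and that between 0 and 11 of the subset are controls or MCI patients, since its make-up by group is not given.

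- First sessions: 22 × 1.5 = 33 hours
- Repeats: 0 to 11 × 1.5 = 0 to 16.5 hours
- Total for participants without dementia: 33 to 49.5 hours

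The documents give no event rates, so no expected count can be calculated.

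**The case against.** The strongest counter-argument is that nothing is actually exempted. Section 10.3 ties the 7/15-day duty to SUSARs, not to Appendix A. Read literally, the SUSAR definition catches any serious event in a person without dementia. The sentence that introduces the list speaks of dementia, so a sensible reader would apply the list only to patients who have it. This defeats one tempting inference: that the protocol settles the matter and takes strokes in volunteers out of expedited review. The documents do not say that Appendix A overrides the definition. It does not remove the conflict, because the introductory sentence explains the list without restricting it, and the appendix itself names no group.

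A reader might also infer that serious events are least expected in controls. The documents do not support that. They give no rates by group, and Section 7.2 has controls matched to patients on age, gender and co-morbidities, with BP matching as well. Controls must lack major co-morbidity, so their risk may be lower, but by how much is not stated. MCI is less clear-cut still: Section 4 describes mixed causes and a raised risk of later dementia.

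Two further objections stand as limits. The 50% counts people under an unclear rule, not events affected. And separating controls and MCI patients from the rest does not address stroke in AlzD patients, whose eligibility criteria exclude substantial cerebrovascular disease; the sponsor may want to consider that separately.

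**Conclusion.** The point holds as an inconsistency in the safety-reporting text. Dementia is the only reference for expectedness, the groups covered are not stated, and for 22 of 44 planned participants the SUSAR definition and Appendix A can point in opposite directions with no rule to decide between them. This rests on the wording and on the eligibility criteria, with no assumed figures.

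The practical reach is small. The loss arises only if Appendix A is followed, and then it is the expedited ethics report alone. Reportable events should be rare in a non-invasive observational study with short sessions, though that is a judgement because the documents give no rates. Sample size, endpoints and analysis are untouched. It is a minor point that is worth correcting because the correction is so cheap.

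**What to change.** Reconcile Section 10.1 and Appendix A by group:

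- In Section 10.1 (Expected Serious Adverse Events/Reactions) and at the head of Appendix A, state that the exemption applies only to participants with a dementia diagnosis, that is, VascD or AlzD.
- In the SUSAR definition, state that for controls and MCI patients expectedness is not judged against dementia, so a listed SAE is not automatically exempt from the 7/15-day report. One workable reference is the participant's recorded medical history, which Section 8.3 already collects for every group; the sponsor may prefer another, provided that it is named.

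The cost is about one sentence in each place, no new data, and at most a rare additional expedited report.
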